## 1.0 Objectives / Specific Aims

### **Aim 1: Determine the effect of in-home use of TheraBracelet on neural plasticity**

- **Hypothesis:** TheraBracelet induces neural plasticity.

### **Aim 2: Determine the effect of in-home use of TheraBracelet on hand function**

- **Hypothesis:** The immediate improvement in hand function with TheraBracelet leads to more use of the affected hand and arm in the home, resulting in hand functional recovery.

## 2.0 Background

More than 4 million stroke survivors in the U.S. suffer from post-stroke sensorimotor hand disability, which is typically permanent and difficult to treat. Hand disability has a profound negative impact on functional ability and independence. One important roadblock to motor recovery is insufficient treatment for sensory deficits. Sensory feedback is integral to nearly all motor control tasks, and sensory deficits exacerbate motor deficits and hinder recovery. The lack of a practical treatment approach for sensory impairment is a critical limitation to the current state of post-stroke hand rehabilitation. While sensory afferent stimulation has been shown to facilitate experience-dependent neural plasticity and motor recovery, existing methods such as transcutaneous electrical nerve stimulation require a 1-2 hour application in a sedentary posture on a daily basis, which is impractical. To address this limitation and fully leverage the therapeutic benefits of sensory stimulation, we have developed “TheraBracelet” that delivers subsensory stimulation via a wearable wristband throughout daily living. It provides the dual benefits of facilitating plasticity and enabling home use to increase the treatment dose substantially beyond typical clinic visits available in the health care system.

TheraBracelet’s imperceptible random-frequency vibration helps other sensory signals from the hand exceed the threshold for sensing (known as stochastic facilitation). The theoretical framework is that enhanced sensory feedback during everyday motor tasks will improve task performance, thus increase hand use in daily living, which will facilitate experience-dependent neural plasticity and hand motor recovery. Our preliminary research has identified an effective device design and a mechanism of action: 1) Immediate improvements in finger sensation and dexterity are observed by turning on the vibration. 2) The effective vibration intensity is 40% below sensory threshold, with higher intensities leading to lesser effects. 3) The vibration can be applied to the wrist because the same benefits were obtained for various vibration locations of the wrist, forearm, dorsum hand, and palm, and the wrist is optimal for a wearable device. 4) The mechanism for enhanced sensation is that TheraBracelet increases cortical sensorimotor network activity and conscious processing of the sensory signal, as evidenced by increased long-latency encephalogram (EEG) evoked potential for fingertip touch.

## 3.0 Intervention to be studied

Intervention to be studied is wearing a device that can deliver TheraBracelet stimulation in daily living. The device will apply TheraBracelet stimulation (i.e., random-frequency vibration to the wrist at 60% of the sensory threshold determined using the staircase method) for the treatment group, and apply no vibration for the control group (placebo).

## 5.0 Inclusion and Exclusion Criteria/ Study Population

### Inclusion Criteria

- Age = 18 or older
- At least 6 months post-stroke
- Fingertip touch sensory deficits as evidenced by the Semmes-Weinstein Monofilament Test score >2.83, 2-Point Discrimination Test score >5mm, or sense of numbness based on verbal report.
- Ability to move an object with the paretic hand
- Ability to put on a watch daily (by him/herself or with help)

### Exclusion Criteria

- Complete upper limb deafferentation (complete upper limb numbness and no touch sensation from the Semmes-Weinstein Monofilament Test and the Two-Point Discrimination test)
- Rigidity (Modified Ashworth Scale=5)
- Upper limb botulinum toxin injection within 3 months prior to enrollment or during enrollment
- Brainstem stroke
- Comorbidity (peripheral neuropathy, orthopaedic conditions in the hand that limit ranges of motion, neurodegenerative conditions such as Parkinson's, Alzheimer, ALS, and MS, compromised skin integrity of the hand/wrist due to long-term use of blood thinners)
- Change in neurological disorder medications during the enrollment
- Concurrent upper extremity rehabilitation therapy
- Language barrier or cognitive impairment that precludes following 3-step instructions or providing consent

Contraindications to MRI and TMS include: pregnancy, epilepsy, history of brain tumor, hardware in the skull or spine (e.g., coils, clips) implantable medical devices (e.g., pacemaker), metal in the body (not compatible with MRI). Participants will still be eligible to participate if they present with any of these contraindications, however, they will be excluded from participating in these tests.

- **Screening:** Eligibility will be determined based on the potential participant's verbal disclosure or standardized clinical assessments. Potential participants will be asked to complete a pregnancy test.
- **Sex/gender:** We will include chronic stroke survivors of all genders and all racial and/or ethnic groups, since stroke occurs in persons of all genders and all racial and/or ethnic backgrounds. We will not exclude people based on sex/gender, racial or ethnic group.

Specifically, for sex, based on the demographic data and stroke surveillance data, approximately the same number of women and men will be recruited for this study. This recruitment is possible because we will recruit from the RESTORE stroke registry that has been developed by the CTTR Core and the RESTORE stroke registry has 48% female and 52% male stroke survivors.

- **Racial and ethnic groups:** Our goal is to construct a participant pool that matches post-stroke survivor distributions in South Carolina. Thus, we have considered the stroke prevalence in each racial and ethnic group together with the racial and ethnic distribution of the population in South Carolina and target enrollment of stroke survivors in each racial and ethnic group accordingly to represent the South Carolina stroke demographics. Recruitment of diverse racial and ethnic groups is possible because the RESTORE stroke registry currently has 42% African-American and 1% Hispanic.
- **Children:** Children under the age of 18 years will be excluded. The rationale for exclusion of children is that stroke predominantly occurs in adults, and stroke is very rare in children. Importantly, these rare cases may actually differ in their etiology from the subjects we propose to study.

## 6.0 Number of Subjects

A total of 40 subjects will be recruited to participate in this study.

## 7.0 Setting

- All activities will be conducted in a Laboratory located on the Medical University of South Carolina campus.

## 8.0 Recruitment Methods

- Subjects will be recruited through the MUSC Registry for Stroke Recovery that has information of 838 stroke survivors who have agreed to be contacted for research (RESTORE, approved MUSC IRB PRO# 37803, [name] PI). The registry is growing every day, as approximately 500 new stroke cases are treated at the MUSC Stroke Center every year. All eligible stroke patients in the inpatient stroke units as well as the outpatient clinic are contacted by a dedicated recruiter of the Center to be enrolled in the registry. In addition to recruiting stroke survivors from the hospital, we recruit stroke survivors from the community by having a dedicated outreach therapist from the Center visit local stroke support group meetings and develop relationships with stroke survivors, caregivers and clinicians, and also by organizing community outreach events such as stroke caregiver summits and stroke recovery community engagement, to establish grassroots connections with stroke survivors and caregivers in the community. The Center also sends newsletters to survivors, caregivers, local clinics and local clinicians to inform them of news, new events and new projects. With this effort, the registry has been growing with >10 new enrollees per month.
- In addition to the registry, advertisement via internet (e.g., South Carolina Research Studies Directory) will be used.

## 9.0 Consent Process

- Consent will be obtained by the study personnel. The consent process will take place in a private room when the potential participant comes to the laboratory on a scheduled time agreed upon between the study personnel and the participant. The content of the consent will be verbally explained to the participant and the participant will be asked to raise any questions and concerns. If the person requests a waiting period, then one will be given. If the person desires to consent immediately, then the person will provide consent immediately.
- For participants who are having a modified protocol due to COVID-19, they will e-consent. Verbal instruction and explanation will be provided over the phone.

## 10.0 Study Design / Methods

- Study design: The study design is a double-blinded randomized controlled study. Subjects will wear the device for at least 8 hours/day every day during their normal activity for a month, during which they will come to the laboratory for weekly evaluation. Subjects will affix the device to the affected wrist using the unaffected hand, similar to wearing a watch. Follow-up evaluation will occur 3 months after. During this time, subjects will not receive other hand therapy. All subjects will be educated at each visit on the importance of using the paretic hand as much as possible in daily living. The device will deliver vibration (treatment) or no vibration (control) all the time. Double-blinding is possible because the treatment vibration is imperceptible (i.e. subthreshold).
- Schedule: Participation in this study will last approximately 4 months. Subjects will come to the laboratory a total of 6 to 9 times. The baseline (1-2) visit will entail the baseline evaluation followed by an introduction to using the device. Then, weekly visits will be for evaluation after using the device for 1, 2, and 3 weeks. The post evaluation (1-2 visits) will occur after using the device for 4 weeks. The follow-up evaluation (1-2 visits) will occur after they stop using the device for 3 months. The baseline, post, and follow up evaluations may be completed in two visits in an effort to reduce fatigue among participants.
- Evaluation: Multi-modal evaluation will be performed as detailed below.
- MRI: One MRI assessment will be performed at baseline. The scan will be 20 minutes in duration. The MRI assessment is to obtain the individual participant's brain anatomy to facilitate subject-specific localization of brain activity.
- EEG: For the EEG assessment, participants will wear an EEG cap on their head. Gel will be applied to individual EEG electrodes with a blunt syringe that does not penetrate the skin (taking approximately 30 min for this preparation). During the assessment, the participant will rest comfortably in a chair and either rest or grip with the fingers. The EEG assessment will take place at baseline, post, and follow-up evaluation session and last approximately 40 minutes including preparation.
- Neural plasticity assessment: Participants will sit on a chair and rest. A TMS coil will be placed on top of the subject's head. The TMS coil location will be moved around slightly to find the 'hotspot' that stimulates neurons with direct monosynaptic projections to the

alpha motoneurons in the spinal cord for the abductor pollicis brevis (APB) muscle, as seen by the evoked potential in the APB (recorded using electromyogram, EMG) immediately after TMS. To record this MEP from the APB muscle, subjects will have the surface EMG electrodes on the skin on top of the APB muscle belly. Noninvasive electrical nerve stimulation will be applied to the participant's wrist via a surface electrode pair, immediately prior to the TMS. This assessment will take place at each evaluation session and last approximately 30 minutes.

- Clinical Assessment: Subjects' clinical upper extremity function scores will be assessed using conventional clinical assessments used in occupational/physical therapy in which participants will be asked to move the affected hand and arm, grasp objects and perform prescribed tasks (e.g., lifting an object off the table, releasing the object into a bin) as quickly as possible. These tests will be videotaped for scoring. The clinical assessments will take place at each evaluation session and last approximately 30 min.
- Biomechanical hand grip control assessment: Subjects will grip an instrumented object, lift the object off a table against gravity, steadily hold the object at a comfortable reaching distance for 5 s, and then slowly and intentionally release the grip until the instrumented object falls. Subjects will repeat this grip-lift-hold-release task 5 times. The biomechanical assessment will take place at baseline, post, and follow-up evaluation session and last ~15 minutes.
- Wear time assessment: Subjects will fill out a self-reported device use log, indicating the time at which they put on and take off the device every day in their home. They will submit the log to study personnel during the weekly visits.
- In-home upper limb use amount assessment: This assessment entails participants wearing accelerometers on both wrists using standard wrist straps for 3 days at baseline, immediately after one month of wearing TheraBracelet, and at follow-up. Subjects will be instructed to wear the accelerometers during the entire day. The wear time assessment will take place at each evaluation session.
- Home therapy program: Participants and their caregivers will meet with study staff to identify specific hand/arm tasks to practice at home. The goal of this program will be to increase hand/arm use in activities of daily living. Participants will document their progress on check-off sheets and submit them during their weekly laboratory visits.
- Due to COVID-19, some participants may be assessed over the phone only, and may continue with the home intervention (home exercise and watch) while being monitored via weekly phone calls until they could come to the laboratory for full assessments.

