## 12.0 Data Management

- Analysis: The primary analysis will be a repeated measures ANOVA for each outcome. The primary independent variables are group (treatment vs. control), evaluation time (baseline and 1-4 weeks of using the device for the primary analysis; follow-up will be included in subsequent analysis), and their interaction. We will also include sex as an independent variable along with its interactions.

- Sample size justification: For the repeated measures design with a significance level of 0.0125 (adjusted for multiple comparisons), at least 80% power, and 5 primary time points, using a standard deviation of 6.4 s and compound symmetry correlation of 0.92 (observed in the pilot study), a sample size of 17 per group will be adequate to detect a minimum difference (futility level) of 7 s. Adjusting for 15% attrition, 20 per group is planned.
- Confidentiality: All data except for the consent forms and HIPPA forms will be de-identified at the time of data recording. All electronic data will be stored in a password-protected research server that is accessible to study personnel only. The server is backed up every day and maintained 24/7 by IT specialists. All paper data with personally identifiable information including the consent forms and HIPPA forms will be stored in a key-locked cabinet in a key-locked room that is accessible to study personnel only. Other paper data without personally identifiable information including testing sheets documenting testing sequences and notes will also be stored in a cabinet in a key-locked room that is accessible to study personnel only.
- Data sharing: Only de-identified coded data will be reported and/or shared with the public and other investigators in publications, in ClinicalTrials.gov, or via network storage.

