## 13.0 Provisions to Monitor the Data to Ensure the Safety of Subjects

The proposed research is a single site pilot clinical trial that is concerned with an intervention using an investigational device in a double-blinded randomized controlled design. A Data Safety Monitoring Board (DSMB) will be used.

- A DSMB will ensure the safety of participants and the validity and integrity of data collected during the tenure of the project. The overall framework involves review of the enrollment/retention and safety and adverse event data by the DSMB during the proposed research.
- DSMB composition: The DSMB will be composed of three professionals with expertise related to the proposed area of study who are not involved with the study design or experiments. Specifically, the DSMB will include: (1) a board-certified stroke neurologist who also is a stroke recovery researcher and is experienced in care of chronic stroke survivors and their recovery; (2) a registered and licensed occupational therapist who also is a quantitative researcher in outcomes measurement and research design; and (3) a biostatistician with expertise in design and analysis of clinical trials. This multidisciplinary group has experience with management and monitoring of clinical intervention trials involving individuals following stroke, and brings substantial expertise adequate to serve as the DSMB.
- DSMB responsibilities: The responsibilities of the DSMB are as follows.
  - Prior to any enrollment, the DSMB will review the study design, protocol, informed consent documents, amendments, recruitment/enrollment plan, statistical analysis plan, and data and safety monitoring plan, and document the agreement or recommendation.

- Once the enrollment begins, the DSMB will convene every 6 months to review the progress of the trial.
- The DSMB will review the enrollment/retention data including new enrollments, progression of the enrollees' participation in the study, any discontinuation of participation in the study with or without adverse events, and the current enrollment status compared to the project time line.
- The DSMB will review data quality and quality control data.

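### Baseline hand function is not adjusted for in the primary group contrast or, as far as stated, used in allocation, so chance baseline differences pass almost whole into the comparison the sample size matches

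*Combined protocol and SAP*

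**What the plan says.** **Allocation.** Section 10.0 says "The study design is a double-blinded randomized controlled study", and section 13.0 repeats the description ("investigational device in a double-blinded randomized controlled design"). Section 6.0 gives a total of 40 and section 12.0 adds "Adjusting for 15% attrition, 20 per group is planned", so a 1:1 target can be inferred. No sequence method, block size or stratification factor is given. Sections 4.0 and 11.0 are not in the text available, so the absence is established only for what can be read.

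**Timing.** Under Schedule, section 10.0 says "The baseline (1-2) visit will entail the baseline evaluation followed by an introduction to using the device". Baseline values therefore exist before the device is worn.

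**Analysis.** Section 12.0 plans a repeated measures ANOVA for each outcome, with group, time and their interaction, plus sex and its interactions. The primary analysis times are baseline and weeks 1 to 4. Baseline is thus an outcome time, not a covariate, and the section does not say which model term is the primary test.

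**Sizing.** Section 12.0 uses a "significance level of 0.0125 (adjusted for multiple comparisons"), "at least 80% power, and 5 primary time points", and sizes the trial "using a standard deviation of 6.4 s and compound symmetry correlation of 0.92 (observed in the pilot study"). It arrives at 17 per group for a 7 s difference, and 20 per group after attrition.

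**The concern.** A correlation of 0.92 under compound symmetry means that 92% of the variance in the timed score is stable difference between people. If one arm starts faster by chance, it stays faster at every visit, and that gap sits inside any comparison of raw group levels. With 17 to 20 per arm, such gaps can be large relative to 7 s.

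The plan already collects the one measurement that would remove most of this variation. In the text available, neither the primary group contrast nor the allocation uses it for that purpose. At stake are the precision of the group comparison and how far its estimate can be trusted in the single trial that is run.

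**Working it through.** **Inputs**, all from section 12.0: SD 6.4 s, correlation 0.92, 5 times, alpha 0.0125, power 80%, difference 7 s, 17 per group. Two assumptions: alpha is two-sided, and 6.4 s is the SD of raw scores at one visit.

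**1. Which comparison does 17 per group fit?**

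- Variance factor for the five-visit mean: (1 + 4 × 0.92)/5 = 0.936.
- SD of that mean: 6.4 × √0.936 = 6.19 s.
- n per group = 2 × [6.19 × (z for alpha/2 + z for power)/7]² = 17.45, which rounds up to 18. Normal-approximation power at 17 is 78.8%; with the t distribution it is 73.8%. A one-sided alpha gives 15.
- Attrition: 17/0.85 = 20, as stated.

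So 17 is close to a comparison of raw levels. Contrasts that remove baseline do not come near it:

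| Contrast | n per group (normal approximation unless noted) |
|---|---|
| Change to week 4 | 3 |
| Change to mean of weeks 1–4 | 2 |
| Baseline as covariate | 2–3 (4–5 with the t distribution) |
| Group-by-time F test | 4–5 |

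**2. How much of a baseline difference passes through?** A baseline difference of b seconds is expected to persist as 0.92b at each later visit. In the five-visit mean it becomes (1 + 4 × 0.92)/5 × b = 0.936b.

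**3. How large can it be by chance?**

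| | 17 per group | 20 per group |
|---|---|---|
| SE of baseline difference, 6.4 × √(2/n) | 2.20 s | 2.02 s |
| 95% range | ±4.30 s | ±3.97 s |
| Part passing into the group term | ±4.03 s | ±3.71 s |
| Chance of a difference above 3.5 s in either direction | 11.1% | 8.4% |

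If 3.5 s goes against treatment, an expected 7 s becomes 7 − 0.936 × 3.5 = 3.7 s.

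**4. What does a baseline covariate do?** Take the mean of weeks 1 to 4, with 17 per group.

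- Unadjusted SD: 6.4 × √[(1 + 3 × 0.92)/4] = 6.4 × √0.94 = 6.205 s; SE = 6.205 × √(2/17) = 2.13 s.
- Adjusted SD: 6.4 × √(0.94 − 0.92²) = 6.4 × √0.0936 = 1.958 s; SE = 1.958 × √(2/17) = 0.67 s.
- The difference detectable at 80% power falls from 7.1 s to 2.2 s.

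**5. Allocation or analysis: which one helps?** Simulations used the plan's inputs with 17 per group. The first three power rows test the group term over all five visits.

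| Allocation | Baseline in model | SE | Power, 7 s at all five visits | Power, 7 s after baseline only |
|---|---|---|---|---|
| Simple | None | 2.12 s | about 74% | 50% |
| Simple | Median-split factor | 1.36 s | about 99% | 91% |
| Stratified at median | Same factor | about 1.35 s | about 99% | 92% |
| Simple | Continuous covariate, weeks 1–4 | 0.68 s | not applicable | about 100% |

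The fourth column is the more realistic one, because the device is introduced after baseline: averaging over five visits dilutes 7 s to 7 × 4/5 = 5.6 s. Stratified allocation without the factor in the model gave 80.6% and 49.7%.

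On balance alone, a median split leaves a fraction 1 − 2/π = 0.363 of the variance of the baseline difference. Its SE falls to 2.20 × √0.363 = 1.32 s, and the chance of a gap above 3.5 s falls from 11% to about 1%.

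**The case against.** The strongest reply is that nothing here is invalid. Simple randomisation is unbiased, and the standard error already includes chance imbalance: simulated type I error was 1.2% to 1.4% against a nominal 1.25%. This stands. A reader might infer that missing stratification biases the result or inflates the error rate; the plan's figures do not support that.

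A second reply is that the planned model contains group by time, in which a constant baseline shift cancels, and that the Aim 2 hypothesis is about improvement and recovery, which is change. This also stands and limits the point to the group term. It does not dispose of it: section 12.0 does not make the interaction the primary test, and its sample size fits the group term instead.

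Third, a reader might infer that the allocation method itself costs the power, and that stratifying would lift it from 74% to 99%. The simulations do not support this. Almost all of that gain comes from putting baseline in the model; with the factor already there, stratified allocation adds 0 to 2 points.

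Finally, the documents name no timed test and give no pilot median, and one timed stratum need not balance other outcomes such as neural plasticity. That is a fair limit on stratification. It does not weaken the case for adjusting each outcome for its own baseline.

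**Conclusion.** The concern holds as a matter of efficiency and of how far a single estimate can be trusted. In the group term that the sample size matches, baseline accounts for about 94% of the sampling variance. A chance gap worth half the target has a probability of about 11% with 17 per group (8% with 20). A baseline covariate cuts the standard error to about a third.

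The fault lies mainly in the analysis section: baseline is unadjusted and the primary contrast is unnamed. Unstratified allocation is a secondary matter.

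The figures rest on the pilot SD and correlation holding in this trial, on compound symmetry, and on two-sided alpha. A lower correlation would shrink both the carry-through and the gain from adjustment.

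**What to change.** **Main change, section 12.0.** Name the primary contrast and adjust it for baseline. Suggested text:

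> The primary contrast is the group difference averaged over weeks 1 to 4, from a repeated measures model with weeks 1 to 4 as outcome times, the baseline value of the same outcome as a continuous covariate, and group, time, their interaction, and sex with its interactions.

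For measures taken only at baseline and post evaluation, such as EEG and grip control, the post value is the outcome. Restate the sample size paragraph for this contrast. The cost is a few sentences; the baseline value is already collected.

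**Optional addition, section 10.0.** Allocate 1:1 in permuted blocks after the baseline evaluation and before the device is introduced, in two strata of baseline time on a named timed clinical measure, with the cut-point fixed in advance. Keep baseline in the model, because stratifying without modelling it makes the test overly conservative. This buys more comparable arms (a gap above 3.5 s falls from about 11% to 1%) and at most about 2 points of power.

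Its costs are a two-stratum list, a time read at the visit rather than later from video, and a stated allocation rule for participants assessed by phone only under the COVID-19 provision.

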## 18.0 Drugs or Devices (if applicable)

- Device: A stand-alone prototype is composed of an MP3-playing watch and a vibrator (see the pictures below; total weight 40g, watch=3.7cm×5.3cm). Both items are off-the-shelf products (i.e. available to purchase for anyone). The vibrator is attached to the wristband of the watch. The vibrator's wire is connected to the MP3 player via an audio jack. The MP3 player drives the vibrator with its internal battery, enabling a full day of use after an overnight charge. The MP3 player/watch is charged using a conventional phone charger. The MP3 player can play any file including the treatment vibration file with white noise vibratory signal at the intensity that is 40% below the sensory threshold (i.e. subthreshold, imperceptible to the participant) and control file with zero amplitude (i.e. no vibration).

- FDA: The use of the vibrator for this proposed purpose of affecting the hand sensation and/or dexterity has not been approved by the FDA.
- The vibrators and watches will be stored in the laboratory and will be provided to the participants by the study personnel.

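### Could an immediate on-device effect pass for recovery, because the plan does not say whether the device runs during the week 1-4 evaluations?

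*Combined protocol and SAP*

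**What the plan says.** Section 10.0 defines the arms by what the device plays: "The device will deliver vibration (treatment) or no vibration (control) all the time". Its schedule puts baseline testing before any exposure: "The baseline (1-2) visit will entail the baseline evaluation followed by an introduction to using the device". The week 1, 2 and 3 visits fall within the month of daily wear, the post evaluation follows four weeks of wear, and follow-up comes three months after wear stops. On the functional tests it says "The clinical assessments will take place at each evaluation session and last approximately 30 min". The TMS assessment is also done at every evaluation. EEG and grip control are done only at baseline, post and follow-up.

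Section 2.0 says that immediate improvements in finger sensation and dexterity "are observed by turning on the vibration". Aim 2 treats that gain as a step on the way to recovery: "The immediate improvement in hand function with TheraBracelet leads to more use of the affected hand and arm in the home". Section 12.0 gives the evaluation times as "baseline and 1-4 weeks of using the device for the primary analysis; follow-up will be included in subsequent analysis".

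None of the assessment descriptions says whether the device is worn, running or removed during testing at weeks 1 to 4.

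**The concern.** The plan names two effects of the vibration: an acute one, present while it is on, and a lasting one, which is what the aims target. Baseline can contain neither. Suppose the device were worn and running at the week 1-4 tests. The treatment arm would then move from off to on between baseline and week 1, while the control arm, whose device plays a zero-amplitude file, would have no such change. Randomisation and blinding would not remove the difference, because it is a real effect of treatment, only not the one the aims describe. The overall group-by-time test does not tell a step at week 1 from a gradual gain.

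At stake would be the meaning of a positive primary result, chiefly for the clinical tests at weeks 1 to 4 and for grip control and EEG at the post evaluation.

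**Working it through.** **1. What the text implies about device status at testing**

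- The sentence about continuous delivery cannot be literal. Section 18.0 has the device charged overnight, and section 10.0 asks for at least 8 hours of wear a day with a log of when it is put on and taken off. The sentence separates vibration from no vibration; it does not describe laboratory visits.
- Both aims concern use in the home. Section 10.0 places wear in ordinary daily activity, and the wear log covers the home.
- The weekly and post evaluations are timed by how long the device has been used. That allows off-device testing and does not require on-device testing.
- The TMS assessment at every evaluation places a stimulating electrode pair on the wrist, so staff have to consider the wristband at each visit. The protocol does not say which wrist or require removal, so this is suggestive only.

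**2. The plan's own sample size**

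Inputs from section 12.0: SD 6.4 s, compound-symmetry correlation 0.92, 5 time points, significance level 0.0125, power 80%, difference 7 s. Two-sided testing is an assumption, since sidedness is not stated.

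- SD of a five-visit mean: 6.4 × √((1 + 4 × 0.92)/5) = 6.19 s.
- n per group (normal approximation): 2 × (6.19 × (2.498 + 0.842)/7)² ≈ 17.45, so 18 against the stated 17. Power at 17 is 78.8%.
- Attrition: 17/0.85 = 20, as stated.

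The stated size therefore agrees, within rounding, with a group main effect averaged over five visits. It does not depend on device status at testing.

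**3. Size of the distortion if the device were on**

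Assume no recovery, a constant acute effect of x seconds at weeks 1 to 4 in the treatment arm only, 17 per group and two-sided 0.0125. The values of x are assumptions.

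- Group-by-time: the squared deviations of (0, x, x, x, x) from their mean sum to 0.8x². Noncentrality = (17/2) × 0.8x² / (6.4² × 0.08) = 2.075x², on 4 and 128 df.
- Week 4 minus baseline: SD = 6.4 × √(2 × 0.08) = 2.56 s; SE = 2.56 × √(2/17) = 0.878 s; noncentrality = x/0.878, on 32 df.
- Group main effect over five visits: mean difference 0.8x; SE = 6.19 × √(2/17) = 2.12 s; noncentrality = 0.8x/2.12, on 32 df.

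| Assumed acute effect | Group-by-time | Week-4 change | Group main effect |
|---|---|---|---|
| 1 s | 7% | 8% | 2% |
| 2 s | 39% | 37% | 4% |
| 3 s | 85% | 77% | 8% |
| 3.5 s | 96% | 90% | 11% |

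Entries are the chance of a significant result with no recovery; the nominal level is 1.25%. Section 12.0 lists group, time and their interaction without saying which term decides, so all three columns are relevant.

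**The case for a change.** The strongest case for acting is that the protocol itself asserts the acute effect, that the design is very sensitive to a constant shift (change-score SD 2.56 s against a 7 s target), and that a short statement of test conditions would cost almost nothing. Wording about time spent using the device gives duration, not status, and staff could differ between visits. The off-device follow-up would not fully settle the matter, because no difference at three months fits either an acute aid or a gain that faded.

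Much of this stands as description. The text does not give device status, the arithmetic is right, and the group-by-time term is a natural reading of the primary test. What does not stand is the step from silence to bias. The large percentages need the device to be running at the tests (or its effect to carry over) and an acute effect of 2 s or more; the documents establish neither. Silence is also weak evidence here: the section numbers available jump from 3.0 to 5.0 and from 10.0 to 12.0, and references 1 to 3 are not cited in the text at hand, so test conditions may be described elsewhere.

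A common off-device interval before every evaluation would not work as a rule. At baseline the device has not been introduced, and at follow-up it has been stopped for three months. Whether a helper or the other hand could feel a vibration described only as "subthreshold, imperceptible to the participant" is a separate blinding question with no figures behind it.

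**Conclusion.** The gap is real but does not call for a change to the plan. It is a detail of test conduct, and no rule in the protocol makes the primary contrast biased. The investigators separate the immediate effect from recovery in their own aims and background, and can be expected to keep the week 1-4 tests comparable with an off-device baseline in both arms. Testing sheets, which section 12.0 already mentions, give them a place to note device status.

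If testing is off-device and the acute effect does not carry over, the distortion is nil. If it is on-device, the chance of a significant result without recovery runs from about 7% (1 s) to 96% (3.5 s) on the group-by-time term and from about 2% to 11% on the group main effect, given the plan's SD and correlation, 17 per group, two-sided 0.0125 and an acute effect that is assumed throughout. The sample size is unaffected. The planned analysis of the three-month follow-up gives partial protection: a difference that persists off-device would support recovery, although its absence would not decide the question.
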